# 5.3 Assessment of Success (Patient questionnaire)

Objectives	Questions	Is the question included in the assessment of success? (Yes/No)	Definition of correctly answered question	Assessment of success
	Q1. Please select the option that best describes your experience with the [patient card: name in the local language] (only for oral methotrexate formulations)?	Yes	Question completed correctly [Answer '1' or '2' is desirable]	A patient is successful for awareness when he/she receives the patient card, and is aware of the
	Q2. How did you obtain the information regarding the existence of the [patient card: name in the local language] (only for oral formulations)?	No; complementary information on source of patient card		
Receipt and Awareness (6 questions)	Q3. Please select the option that best describes your experience with the methotrexate package leaflet	Yes	Question completed correctly [Answer '1'is desirable]	boxed warining in the packaging leaflet and visual reminder on the outer packaging (desirable answers).
	Q4. How did you obtain the information regarding the existence of the boxed warning on the methotrexate package leaflet?	No; complementary information on source of package leaflet knowledge		Success for awareness if ≥80% of patients are successful.
	Q5. Please select the option that best describes your experience with the methotrexate outer packaging of oral and parenteral methotrexate-containing products	Yes	Question completed correctly [Answer '1'is desirable]	

Template No.: RWI\_TP\_EPI0016 Revision 1 Reference: RWI\_WI\_EPI0005

Effective Date: 15Jun2018

Page 90 of 92

	Q6. How did you obtain the information regarding the existence of the visual reminder on when to use/take methotrexate?	No; complementary information on source of visual reminder on the outer packaging		
	Q7. According to your knowledge about the purpose of the [patient card: name in the local language] (only for oral methotrexate formulations), please indicate if you agree or disagree with the following statements	Yes	Question completed correctly (6 sub-questions [3 False and 3 True])	A patient is successful for knowledge when he/she scores at least 20 out of 25 points (80%) for questions, including sub-questions, which are completed with correct/desiable answers.  Success for knowledge if ≥ 80% of patients are successful.
Knowledge	Q8. According to your knowledge about the safety measures on the outer packaging of oral and parenteral methotrexate-containing products, please indicate if you agree or disagree with the following statements	Yes	Question completed correctly (4 sub-questions [2 False and 2 True])	
(13 questions)	Q9. Did your pharmacist write the weekday for intake in the respective box of the reminder on the methotrexate packaging?	No; complementary information on packaging reminder		
	Q10. According to your knowledge about the conditions of use for methotrexate, please indicate if you agree or disagree with the following statements.	Yes	Question completed correctly (6 sub-questions [3 False and 3 True])	
	Q11. According to your knowledge about methotrexate, which of the following symptoms are associated with methotrexate overdose?	Yes	Question completed correctly (9 sub-questions [2 False and 7 True])	

Template No.: RWI\_TP\_EPI0016 Revision 1 Reference: RWI\_WI\_EPI0005

Effective Date: 15Jun2018

Page 91 of 92

Q12. How did you gain an understanding about the dosing instructions for once weekly methotrexate?	No; complementary question on source of understanding about the dosing instructions	
Q13. How did you gain an understanding about the risks (side-effects, risk of overdose etc.) associated with taking methotrexate?	No; complementary question on source of understanding about the risks	
Q14. What helps you to remember to take methotrexate as a once-weekly dose?	No; complementary question on reminders set by patients	
Q15. How would you describe your experience with the [patient card: name in the local language]?	No; complementary information on user friendliness of patient card	
Q16. How would you describe your experience with the visual reminder for taking/using methotrexate/ noting down the day of the week to take methotrexate on the outer packaging?	No; complementary information on user friendliness of packaging	
Q17. How would you describe your experience with the information provided in the boxed warning in the methotrexate package leaflet?	No; complementary information on user	

Template No.: RWI\_TP\_EPI0016 Revision 1 Reference: RWI\_WI\_EPI0005

Effective Date: 15Jun2018

Page 92 of 92

	friendliness of packaging	-
Q18. According to your experience please indicate if you have ever accidently taken the once-weekly dose of methotrexate as a daily dose	No; complementary question on patient experience	
Q19. According to your experience please indicate for which reason(s) you took the once-weekly dose of methotrexate as a daily dose?	No; complementary question related to Q18	

Template No.: RWI\_TP\_EPI0016 Revision 1 Reference: RWI\_WI\_EPI0005

Effective Date: 15Jun2018

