  - 3.3. a) Awareness and knowledge of the visual reminder on the packaging of oral and parenteral MTX-containing products; b) Awareness and knowledge of the boxed warning in the package leaflet.

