## 9.5 Study Size

## 9.5.1 Target Sample Size Calculations

The sample size formula based on the normal approximation to the binomial is the following:

$$n = \frac{P \cdot (1-P) \cdot \left(Z_{1-\alpha/2}\right)^2}{e^2},$$

Where P is the expected proportion, and e is the precision or the desired margin of error reflecting how many percentage points the results will differ from the real population value. For example, a 95% confidence interval (CI) with an 8% margin of error means that the statistic will be within 8 percentage points of the real population value 95% of the time. Z1-  $\alpha/2$  is the standard normal Z value corresponding to a cumulative probability of  $1-\alpha/2$  and reflecting the confidence level that will be used (e.g. if  $\alpha$  =.05 (i.e. 5% level of significance) then Z = 1.96). The range of p is between 0 to 1, and therefore the range of p(1-p) is between 0 to 1. The value of p that maximises p(1-p) is p = 0.5. Consequently, if there is no information available to approximate p, then p = 0.5 (i.e. 50%) can be used to generate the most conservative i.e. largest sample size.

Table 3 Margin of Error for 95% CI Based on Various Sample Sizes and Proportions of Interest

Margin of error for 95% CI (absolute precision)									
Proportion	8%	7%	6%	5%	4%	3%	2%		
10%	55	71	97	139	216	384	864		
30%	127	165	225	323	504	896	2,017		
50%	150	196	267	384	600	1,067	2,401		
70%	127	165	225	323	504	896	2,017		
90%	55	71	97	139	216	384	864		

Template No.: RWI\_TP\_EPI0016 Revision 1 Reference: RWI\_WI\_EPI0005

Protocol/Study No: SC02 EMA/2018/19/PE

Page 41 of 92

30

30

30

30

30

150

CI = confidence interval.

In each target population (prescribers, pharmacists and patients) the sample of 150 completed questionnaires can provide for a given proportion 50% and a confidence interval of 95% with a precision of 8%, i.e. that proportion in the target population could be between 42% and 58%. This sample (150) will be split among 5 countries for each of the surveys.

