## Assessment of success

In each of the 3 surveys, the proportion of correct or desirable responses across all questions related to the evaluation of the objectives of the surveys will be considered to assess the success.

Template No.: RWI\_TP\_EPI0016 Revision 1 Reference: RWI\_WI\_EPI0005

Protocol/Study No: SC02 EMA/2018/19/PE

Page 46 of 92

The questions considered as complementary will not be included in the assessment of success. The details of the assessment of the success for each survey and each objective is described in Annex 5.

Success at the prescriber, pharmacist, patient level will be defined for each objective based on the number of sub-questions related to that objective being answered correctly or desirably. It is proposed to set the threshold to at least 80% of knowledge questions, including sub-questions, are completed with correct/desirable answers. .

A threshold of 80% successful prescribers/pharmacists/patients on each of the outcomes of awareness, knowledge and self-declared behaviour (self-declared behaviour is not for patients) would be considered appropriate for assessing the effectiveness of RMM.

If additional information from published literature becomes available at the time of reporting, then the results will be discussed in the context of this new information. The methods of reporting and analysis of results obtained will be done as already described in the Protocol and will be further detailed in the SAP.

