# **ANNEX 5. ASSESSMENT OF SUCCESS**

# 5.1 Assessment of Success (Prescriber questionnaire)

Objectives	Questions	Is the question included in the assessment of success? (Yes/No)	Definition of correctly answered question	Assessment of success
	Q1. Please select the option that best describes your experience with the [Direct Healthcare Professional Communication (DHPC): country-specific name] distributed on [country-specific date of distribution] for methotrexate formulations?	Yes	Question completed correctly [Answer '1' or '2' is desirable]	A prescriber is successful for receipt and awareness when he/she receives the DHPC, the HCP guide, the HCP checklist (desirable answers) and is aware of the patient card (desirable answers).  Success for receipt and awareness if ≥80% of prescribers are successful
Receipt and Awareness (5 questions)	Q2. Please select the option that best describes your experience with the [HCP guide: country-specific name] distributed on [country-specific date of distribution]?	Yes	Question completed correctly [Answer '1' or '2' is desirable]	
	Q3. Please select the option that best describes your experience with the [HCP checklist: country-specific name] distributed on [country-specific date of distribution]?	Yes	Question completed correctly [Answer '1' or '2' is desirable]	
	Q4. Please select the option that best describes your experience with the [patient card: name in the local language] (for oral methotrexate formulations)?	Yes	Question completed correctly [Answer '1' or '2' or '3' is desirable]	

Template No.: RWI\_TP\_EPI0016 Revision 1 Reference: RWI\_WI\_EPI0005

Effective Date: 15Jun2018

Page 85 of 92

Objectives	Questions	Is the question included in the assessment of success? (Yes/No)	Definition of correctly answered question	Assessment of success
	Q5. In your daily practice, what version of the educational materials (EM) related to methotrexate do you use?	No; complementary information on mode of distribution		
Knowledge (1 question)	Q6. According to your knowledge about the conditions of use for methotrexate, please indicate if you agree or disagree with the following statements.	Yes	Question completed correctly (16 sub-questions [10 False and 6 True])	A prescriber is successful for knowledge when he/she scores at least 13 out of 16 points (80%) for sub-questions that are correctly answered.  Success for knowledge if ≥ 80% of prescribers are successful.

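### The awareness verdict requires every measure to be passed at once, which sets an unstated bar of about 89% to 93% per measure under independence and does not show which measure fell short

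*Protocol*

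**What the plan says.** Section 8 lists the measures as separate elements. For prescribers, the DHPC is 1.1 and the educational materials with the patient card are 1.4. For patients, the card is 3.1, and 3.3 asks for "Awareness and knowledge of the visual reminder on the packaging of oral and parenteral MTX-containing products; b) Awareness and knowledge of the boxed warning".

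Section 9.7.2.2 (Assessment of success) then says: "Success at the prescriber, pharmacist, patient level will be defined for each objective based on the number of sub-questions related to that objective"; what is counted is correct or desirable answers. At population level the criterion for judging effectiveness is "A threshold of 80% successful prescribers/pharmacists/patients on each of the outcomes of awareness, knowledge and self-declared behaviour". For knowledge, a respondent succeeds with 80% of sub-questions right (13 of 16, 8 of 10 or 20 of 25 in Annex 5).

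Annex 5 gives awareness no such tolerance:

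- Patients (5.3): the rule opens with "A patient is successful for awareness when he/she receives the patient card, and is aware of the", and its two remaining items are given as "boxed warining in the packaging leaflet and visual reminder on the outer packaging (desirable answers"). The verdict is "Success for awareness if ≥80% of patients are successful".
- Prescribers (5.1): "A prescriber is successful for receipt and awareness when he/she receives the DHPC, the HCP guide, the HCP checklist (desirable answers) and is aware"; the fourth required item is awareness of the card.
- Pharmacists (5.2): aware of both the card and the visual reminder.

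Section 9.7.2.2 also plans the percentage of respondents who received or are aware of the materials and the percentage correct on each question, with 95% CIs for endpoint variables. None of these percentages has its own success threshold.

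**The concern.** The study's aim is the effectiveness of product-specific measures, but the only awareness criterion applies to the conjunction of them. If the joint rate reaches 80%, every measure has reached at least 80%, so a success verdict is informative. A failed verdict is not: it arises when one measure was missed by many respondents, and it can also arise when every measure was known to well over 80%. For example, if 70% of patients had the card and 95% had seen the boxed warning, awareness would fail with no conclusion on the warning.

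The strictness of the rule also depends on how many items a respondent faces, because each added item can only lower the joint rate. The same 80% is therefore a different demand for pharmacists, patients and prescribers.

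**Working it through.** **Inputs.** Respondents per survey n = 150 (section 9.5.1). Items required: k = 3 for patients (Q1, Q3, Q5), k = 2 for pharmacists (Q1, Q3), k up to 4 for prescribers (Q1 to Q4), all from Annex 5. Verdict threshold 80%. The protocol gives no expected awareness per measure and no correlation between items. Both are assumed below and shown over a range.

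**1. The plan's own figure.** Section 9.5.1 states that "the sample of 150 completed questionnaires can provide for a given proportion 50% and a confidence interval of 95% with a precision of 8" per cent. n = P(1−P)z²/e² = 0.25 × 1.96² / 0.08² = 150.06, which agrees with 150.

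**2. Count needed.** 0.80 × 150 = 120 successful respondents, unweighted.

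**3. What holds without any correlation assumption.** The joint rate J lies between 1 − k(1−p) and p when every measure has rate p, and never exceeds the lowest rate. At p = 0.85, J lies in 55–85% for three items and 70–85% for two.

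**4. Implied bar under independence.** J = p^k = 0.80 requires p = 0.80^(1/k):

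- two items: 0.80^(1/2) = 89.4%
- three items: 0.80^(1/3) = 92.8%

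Positive correlation lowers these figures.

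**5. Chance of a success verdict.** Model: one common factor with latent (probit) correlation ρ, so J = ∫ Φ((Φ⁻¹(p) − √ρ·f)/√(1−ρ))^k φ(f) df. The chance of success is P(X ≥ 120) with X ~ Binomial(150, J).

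| ρ | Patients, 85% each: J | chance | Patients, 90% each: J | chance | Pharmacists, 85% each: J | chance |
|---|---|---|---|---|---|---|
| 0 | 61.4% | <0.1% | 72.9% | 2.8% | 72.3% | 1.9% |
| 0.3 | 65.9% | <0.1% | 75.8% | 13.3% | 74.2% | 5.9% |
| 0.5 | 69.2% | 0.2% | 78.2% | 33.3% | 75.8% | 13.2% |
| 0.7 | 73.1% | 3.3% | 81.0% | 67.2% | 77.8% | 29.8% |
| 0.9 | 78.4% | 36.2% | 85.0% | 96.3% | 80.8% | 65.0% |
| 1 | 85.0% | 96.2% | 90.0% | >99.9% | 85.0% | 96.2% |

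Judged alone, a single measure at 85% reaches 120 of 150 with probability 96.2%.

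**6. Which items apply.** Table 1 lists the HCP checklist as not applicable in France and Greece and the HCP guide as not applicable in Germany. Its note 1 says that in Poland the two are one document. Four separate prescriber measures therefore exist only in Sweden (indicatively 30 of 150); elsewhere there are three. Section 7.2 restricts the patient card to oral formulations, while eligibility covers oral and parenteral users. The success column of Annex 5 makes no allowance for any of this.

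**The case against.** The strongest reply is that the rule is coherent and prespecified: a respondent counts only if the whole package reached him or her, and 80% is set for that outcome. This stands to the extent that section 9.7.2.2 attaches 80% to the awareness outcome and nowhere to a single measure. A reader might infer that measures at 85% exceed the protocol's own standard and are nevertheless failed. The documents do not support that wording, because no per-measure standard exists.

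Second, the objectives ask for the extent of awareness, and per-question percentages are planned. A boxed warning seen by 95% would appear in the report as 95%. So it would be wrong to say that elements 1.1, 1.4, 3.1, 3.3a and 3.3b are left unanswered. What is missing is a success criterion for them.

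Third, a reader might infer from the independence row that failure is nearly certain. That depends on an assumed correlation. Items answered by the same person may well be positively correlated, and the table shows how quickly the chance of success then rises, especially for pharmacists.

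Fourth, a four-item calculation for 150 prescribers would describe no survey in this protocol, so none is given. A reader might also infer that prescribers in France, Greece and Germany fail automatically. The questionnaires are stand-alone documents that are not shown and may route around inapplicable items; all that can be said is that Annex 5 does not.

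The reply does not supply a reason for the strictness, or for tolerating 20% errors in knowledge and none in awareness.

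**Conclusion.** The point holds in a limited form. The awareness verdict is tied to an all-items rule whose joint rate is capped by the weakest measure. Under independence it demands about 89% (two items) or 93% (three items) on every measure, and less if items are correlated. The protocol neither states nor justifies that bar.

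If each of three patient measures stood at 85%, the chance of a success verdict would be under 0.1% to 3% for latent correlation 0 to 0.7 and about 36% at 0.9. For pharmacists it would be 2% to 30% over 0 to 0.7.

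These figures rest on equal awareness per measure, all items applicable, 150 respondents and no weighting. Section 9.5.3 gives precedence to country-weighted results, which would change the probabilities. The cap in step 3, the missing allowance for inapplicable items and the lack of any criterion per measure do not depend on these assumptions.

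**What to change.** In the awareness rows of Annex 5 (5.1, 5.2 and 5.3) and in the matching sentence of section 9.7.2.2, apply the 80% criterion to each measure separately, among respondents to whom it applies, with its 95% CI:

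- prescribers: DHPC, guide and/or checklist as distributed in the country, patient card
- pharmacists: patient card, visual reminder
- patients: patient card (oral users), boxed warning, visual reminder

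Report the proportion aware of all applicable measures alongside, as a descriptive figure.

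Questions, data and sample size stay the same; the rewording and the table shells are the work. There are two costs. First, each group gets several awareness verdicts, so the report must state which measures met 80%. Second, measures limited to some countries have fewer respondents. For the checklist (Germany, Poland, Sweden; indicatively 90), the 95% half-width at 80% is 1.96 × √(0.8 × 0.2/90) = 8.3 points, against 6.4 points with 150. Because section 9.5.3 leaves subsamples unweighted, the revised text should also say whether such a verdict uses the weighted or the unweighted proportion.

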- Patient card (only oral MTX formulations) with information on once-weekly dosing regimen and space to write the day of the week
- Update of existing EMs for healthcare professionals (HCPs) (i.e. checklist or guide) (only oral MTX formulations)
- Direct healthcare professional communication (DHPC)

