#### 9.2.2 Inclusion Criteria

The following criteria must be met in order to be enrolled in the study:

- For prescriber questionnaire: Prescribers who have prescribed MTX in a single low dose once a week for indications that require weekly dosing in the past 3 months
- For pharmacist questionnaire: Pharmacists who have dispensed MTX in a single low dose once a week for indications that require weekly dosing in the past 3 months
- For patient questionnaire: Patients who have been treated with a single low dose once a week for indications that require weekly dosing in the past 3 months

Template No.: RWI\_TP\_EPI0016 Revision 1 Reference: RWI\_WI\_EPI0005

Protocol/Study No: SC02 EMA/2018/19/PE

Page 31 of 92

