### 9.3.2.3 Variables collected through the patient survey

The following variables are collected through the patient survey:

- Variables related to the patients treated with MTX
  - Patient age range
  - o Gender (if available)
  - Length of MTX treatment
  - o Indication for MTX treatment
  - o Prescriber setting (at first prescription) and prescriber specialty (at first prescription and in case of prescriber switching)
  - Mode of administration of MTX-containing products (oral/parenteral)
- Variables related to the patient card:
  - o Receipt and awareness of the patient card
  - o Knowledge of the purpose of the patient card
- Variables related to patient's awareness of the boxed warning in the package leaflet
- Variables related to patient's awareness of the visual reminder on the outer packaging of oral and parenteral MTX-containing products

Template No.: RWI\_TP\_EPI0016 Revision 1 Reference: RWI\_WI\_EPI0005

Protocol/Study No: SC02 EMA/2018/19/PE

Page 38 of 92

- Variables related to patient's knowledge of the once-weekly dosing frequency of MTX in the treatment of inflammatory diseases:
  - Knowledge of the once-weekly dosing frequency of MTX in the treatment of inflammatory diseases for his/her indication
  - Knowledge of the boxed warning in the package leaflet and visual reminder on the packaging of oral and parenteral MTX-containing products
  - Knowledge of symptoms of MTX overdose

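### Annex 5.3 scores every patient on an oral-only patient card, with no rule for eligible parenteral users

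*Protocol*

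**What the plan says.** Section 9.2.2 of the protocol admits "Patients who have been treated with a single low dose once a week for indications that require weekly dosing in the past 3 months", with no limit by route. Objective 3 in Section 8 covers both oral and parenteral products. Section 9.3.2.3 lists route of administration among the variables collected from patients.

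Section 7.2 describes one of the measures as "Patient card (only oral MTX formulations) with information on once-weekly dosing regimen and space to write the day of the week". The leaflet warning and the visual reminder on the packaging carry no such limit.

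Annex 5.3 sets the two patient success rules:

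- **Awareness.** "A patient is successful for awareness when he/she receives the patient card, and is aware of the" boxed warning in the leaflet and the visual reminder on the outer packaging. The scored items are Q1 (card), Q3 (leaflet) and Q5 (packaging).
- **Knowledge.** A patient passes "when he/she scores at least 20 out of 25 points (80%) for questions, including sub-questions". The scored items are Q7 (purpose of the card), Q8 (packaging), Q10 (conditions of use) and Q11 (overdose symptoms).

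Q1 and Q7 are labelled as concerning oral formulations only, whereas Q5 and Q8 name both routes. Neither rule has a route-specific version or a not-applicable category. Section 9.7.2.2 takes 80% successful patients on each outcome as the criterion for effective risk minimisation and refers to Annex 5 for the details.

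**The concern.** Part of each patient verdict rests on a measure never intended for some of the eligible patients. A parenteral-only user can know everything addressed to them and still be counted as a failure. The two verdicts would then depend partly on the mix of routes in the panel, when they are meant to reflect how well the measures worked.

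Weighting does not remove this, because the weights in Section 9.5.3 adjust for country and target population, not for route. Since Annex 5.3 states the cut-offs itself, the problem lies in text that is already fixed and is not a detail left for the SAP.

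**Working it through.** **Inputs.** Points from Annex 5.3: Q7 has 6, Q8 has 4, Q10 has 6 and Q11 has 9. The mark is 20 of 25. The success threshold is 80% (Section 9.7.2.2) and the planned sample is 150 patients (Section 9.5.1). The share of parenteral users is not given, so a range is assumed.

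**Step 1: the plan's own figure.** 6 + 4 + 6 + 9 = 25, and 0.80 × 25 = 20. The mark reproduces exactly.

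**Step 2: awareness.** All three items must have a desirable answer. A patient who neither received nor heard of a card has none to give on Q1, so fails whatever the answers to Q3 and Q5.

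**Step 3: knowledge, if Q7 is withheld or scored zero.** The maximum is 25 − 6 = 19, and 19/25 = 76%. This is below 20, so a pass is impossible. Section 9.7.2.2 defines the individual score over all knowledge questions, so nothing written there shrinks the denominator.

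**Step 4: knowledge, if Q7 is asked of everyone.** The maximum stays at 25. Assume a parenteral user guesses the six agree/disagree items independently, each with probability 0.5. With s points on the other 19, the user needs r = 20 − s from Q7. The chance of a pass is P(X ≥ r) with X ~ Binomial(6, 0.5).

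| Score on the other 19 | Needed from Q7 | Chance of passing |
|---|---|---|
| 19 | 1 | 63/64 = 98.4% |
| 18 | 2 | 57/64 = 89.1% |
| 17 | 3 | 42/64 = 65.6% |
| 16 | 4 | 22/64 = 34.4% |
| 15 | 5 | 7/64 = 10.9% |

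A user with 16/19 = 84.2% on the applicable items is already above the 80% standard, yet passes only about one time in three.

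**Step 5: effect on the overall verdict where all parenteral users fail an outcome.** Let q be their share. Overall success = (1 − q) × success among oral users, which is at most 1 − q. To reach 80%, oral users need 0.80/(1 − q).

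| Assumed q | Ceiling on overall success | Success needed among oral users |
|---|---|---|
| 10% | 90% | 88.9% |
| 20% | 80% | 100% |
| 30% | 70% | not attainable |
| 50% | 50% | not attainable |

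In the unweighted sample, 20% is 0.20 × 150 = 30 patients. Section 9.5.3 gives precedence to weighted results, so there q is the weighted share.

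**Step 6: a mark on the applicable items.** 0.80 × 19 = 15.2. The smallest whole score that meets 80% is therefore 16 (84.2%), since 15/19 is 78.9%.

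**The case against.** The strongest reply is that the protocol does not say who is shown Q1 and Q7. The oral-only label may route the question or merely describe the card; the pharmacist Q1 in Annex 5.2 has a similar label that reads as description. Section 9.7.4 says participants cannot skip questions, while Sections 9.6.1 and 9.8.1 mention skip patterns. The routing would be in the stand-alone patient questionnaire, which is not shown. A reader might infer that parenteral users can never pass knowledge. The document supports that only if Q7 is withheld or scored zero; otherwise the effect is distortion, not a ceiling.

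A reader might likewise infer that every parenteral user fails awareness. That does not follow. Q1 accepts two answers whose texts are not shown, and Section 9.7.2.2 counts receipt or awareness of the card, or both. Some patients may also hold a card from earlier or concurrent oral use.

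Two further points on that side are fair. Results by country are descriptive, so to say that country comparisons are confounded goes further than the plan; a different route mix could still shift the country figures. And Section 9.7.2.2 leaves further detail to the SAP, where an unasked Q7 could be handled.

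These points limit how certain and how large the effect is. They do not supply the missing rule: Annex 5.3 as written gives one mark of 20/25 and one awareness rule to all patients, and neither reading of the routing makes card items a fair measure for someone who only injects.

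**Conclusion.** The point stands in conditional form. Annex 5.3 misclassifies parenteral-only patients against the protocol's own effectiveness criterion.

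- **Awareness:** failure follows for those who never received or heard of a card. It is likely, but not certain, for parenteral users as a group.
- **Knowledge:** a pass is impossible (19 against 20) if Q7 is withheld or scored zero. If Q7 is asked of everyone, the result depends in part on answers about a card not meant for that patient, with pass chances from 34% to 89% for scores of 16 to 18 on the applicable items, if those answers are guesses.
- **Overall verdict:** the ceiling of one minus the parenteral share applies to an outcome only where all parenteral users fail it. The document does not support a flat statement that the 80% threshold cannot be reached, because both the routing and the share are unknown.

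The rule should be settled before success is scored, since a primary-objective verdict depends on it.

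**What to change.** Amend Annex 5.3 to score by the route of administration already collected:

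- **Parenteral-only patients:** leave out Q1 and Q7. Judge awareness on Q3 and Q5, and knowledge as at least 80% of the 19 points on Q8, Q10 and Q11, which is 16 of 19.
- **Patients using oral methotrexate, alone or with parenteral:** keep the current rules.
- **Reporting:** give card receipt, card awareness and Q7 among oral users only, and show both success verdicts by route as well as overall.

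State also whether parenteral-only patients are shown Q1 and Q7. Under the scoring above the verdicts are the same either way, so the change works even if the questionnaire is already programmed.

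The cost is a rewording of Annex 5.3, carried into the SAP, with no new data. The downside is two knowledge cut-offs to explain, and whole-number scoring makes the parenteral one slightly stricter (84% against 80%). Results by route would be unweighted under Section 9.5.3 and should be labelled so.
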